3.1 Study design

This study uses а 2-treatment arm, randomized, parallel-group, double-blind, placebo-controlled design in patients with PsA and axSpA. The dosing of secukinumab will be applied according to the approved European Summary of Product Characteristics (SmPC) in PsA and AS disease. In case of axSpA patients with objective signs of inflammation at screening, evident by either MRI with Sacroiliac joint inflammation (according to source documentation) and/or hsCRP > upper limit of normal (ULN, as defined by central lab), secukinumab/placebo will be applied as 1 (1.0 mL pre-filled syringe (PFS) of 150 mg dose) s.c. injection. At Baseline approximately 200 patients will be randomized. Randomization will occur to 1 of the following 2 treatment groups in a ratio of 1:1:

- Group 1 (secukinumab): secukinumab as 1 (1.0 mL pre-filled syringe (PFS) of 150 mg dose) s.c. or 2 (2 x 1.0 mL PFS of 150 mg dose, 300 mg) s.c. injections according to axSpA or PsA disease (including extent of psoriasis and TNF-inhibitor status) at Baseline, Weeks 1, 2, and 3, followed by administration every 4 weeks starting at Week 4.
- Group 2 (placebo): placebo as 1 (1.0 mL PFS) or 2 (2 x 1.0 mL PFS) s.c. injections according to axSpA or PsA disease (including extent of psoriasis and TNF-inhibitor status) at Baseline, Weeks 1, 2, 3, followed by administration every 4 weeks starting at Week 4.

Additionally, it is planned to enroll no more than 40% TNF-IR patients in the study.

Starting at Week 24, patients who have been randomized to placebo at Baseline will all switch to secukinumab. They will receive the dose according to their disease (PsA or axSpA). Therefore they will receive secukinumab 150 mg (1.0 mL PFS of 150 mg dose s.c.) or 300 mg (2 x 1.0 mL PFS of 150 mg dose s.c.). Secukinumab will be administered without a loading phase every 4 weeks (Figure 3-1). Thus, starting at Week 24, patients in both groups will receive secukinumab either 150 mg or 300 mg as 1 or 2 injections of 1 mL/150 mg in PFS in an open-label fashion until Week 52 (last dose given at Week 48). However, original randomized treatment assignment to secukinumab or placebo will remain double-blinded to all patients, investigators, and site personnel, whereas the Sponsor (including the Region Europe Clinical Team, statisticians and data management) will be unblinded after the Week 24 database lock (see Section 3.5) and analyses are completed (see Section 9.7).

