9.4.2 Statistical model, hypothesis, and method of analysis

The null hypothesis to be rejected is that the odds of response Week 24 are equal in both treatment groups. The corresponding alternative hypothesis is that the odds of response at Week 24 are higher under secukinumab compared to placebo.

Let pj denote the proportion of responders at Week 24 for treatment group j, j=0, 1, where

- 0 corresponds to placebo
- 1 corresponds to secukinumab

The following hypotheses will be tested:

H0: (p1 / (1 - p1)) / (p0 / (1 - p0)) = 1 versus HA: $(p1 / (1 - p1)) / (p0 / (1 - p0)) \neq 1$

In other words:

HA: The odds ratio of achieving a response at Week 24 for secukinumab vs Placebo is different from 1.

The primary analysis will be performed comparing treatments with respect to the primary efficacy variable in a logistic regression model with the factors treatment, $TNF\alpha$ inhibitor status and stratification factor diagnosis (PsA or axSpA). The odds ratio and its 95% confidence interval and p-value will be given.

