9.4.4 Sensitivity analyses

A possible effect modification of patient characteristics will be explored by subgroup analyses for sex, age class, $TNF\alpha$ inhibitor status and disease severity at Baseline. The primary model

may also be recalculated with these factors included as well as with respective terms for a subgroup*treatment interaction. In case of a substantial number of missing values, alternative approaches to handle missing values (RMREM, MI) may be additionally calculated as sensitivity analyses.

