9.8 Sample size calculation

The primary endpoint of this trial is the percentage of patients with resolution of Achilles tendon enthesitis assessed by application of firm pressure with the pulp of the thumb by the physician at Week 24. The sample size calculation is based on the same enthesitis assessment we performed within the FUTURE 2 PsA trial (CAIN457F2312) in the form of the LEI which is composed of three different enthesial sites (Lateral epicondyle, left and right; Medial femoral condyle, left and right; Achilles tendon insertion, left and right). Within this trial, the resolution of enthesitis amongst those patients with these symptoms at Baseline has been assessed for Week 24:

Week 24, the end of the placebo-controlled phase:

- Secukinumab (300 mg): 48.2% of patients.
- Secukinumab (150 mg): 42.2% of patients.
- Placebo: 21.5% of patients.

In addition to these clinical data we can make the following assumptions:

- There is no difference in response to secukinumab between the different enthesial sites assessed as part of the LEI in the FUTURE 2 trial. Therefore we do not expect a different response when we only assess the Achilles tendon insertion.
- There is no difference in secukinumab response rates regarding resolution of enthesitis between PsA and axPsA patients. Therefore we pool the analysis for both diseases.

A total of 89 patients per arm are required to achieve 90% power to detect a difference on a two-sided, 5% significance level, if the true response rates are 45% under secukinumab and 21% under placebo. To account for some drop-outs and other protocol violations, 100 patients per arm = 200 patients total should be recruited into this trial.

For the comparison within the 2 subgroups of PsA and axSpA patients, which will consist of approximately 50% of the total study population each, the trial will have about 58% power with regard to the primary endpoint.

10 Ethical considerations

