## **Analysis of secondary efficacy variables**

- Heel pain**

The mean change from Baseline of heel pain at 24 weeks, measured on a 10-point NRS will be analyzed using an Analysis of covariance (ANCOVA) model with factors treatment, country and diagnosis (PsA or axSpA) and with covariate baseline measurement of heel pain. The adjusted (LS) mean difference will be calculated as a point estimate together with its corresponding 95% confidence interval and p-value.

- Bone marrow oedema (PsAMRIS)**

The percentage of patients with an improvement of bone marrow oedema will be analyzed using a logistic regression model with factors treatment, country and diagnosis (PsA or axSpA). The odds ratio and its 95% confidence interval (CI) and p-value will be presented comparing secukinumab to placebo at Week 24.

- Enthesitis Assessment (LEI)**

The 4-site LEI (i.e. score with the four correct sites: lateral epicondyle humerus L + R and proximal achilles L + R) will be analyzed using a logistic regression model with factors treatment, country and diagnosis (PsA or axSpA). The odds ratio and its 95% confidence interval (CI) and p-value will be presented comparing secukinumab to placebo at Week 24.

- Physician's global assessment of disease activity**

Physician's assessment, measured on a VAS scale will be analyzed using an ANCOVA model with factors treatment, country and diagnosis (PsA or axSpA) and with covariate baseline value of global assessment of disease activity. The adjusted (LS-) mean difference will be calculated as a point estimate together with its corresponding 95% confidence interval and p-value.

- Physician's global assessment of heel enthesiopathy activity**

Physician's assessment, measured on a VAS scale will be analyzed using an ANCOVA model with factors treatment, country and diagnosis (PsA or axSpA) and with covariate baseline measurement of the global assessment of heel enthesiopathy. The adjusted (LS-) mean difference will be calculated as a point estimate together with its corresponding 95% confidence interval and p-value.

- Patient's global assessment of disease and heel enthesiopathy activity**

Refer to section 2.11 for analyses details.

- SF-36 or SF-36v2**

Refer to section 2.11 for analyses details

The time courses of secondary endpoints (percentage of patients with resolution of enthesitis as assessed by LEI, mean change from baseline for heel pain in NRS, Physician's / patient's

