## **3 Sample size calculation**

The primary endpoint of this trial is the percentage of patients with resolution of Achilles tendon enthesitis assessed by application of firm pressure with the pulp of the thumb by the physician at Week 24. The sample size calculation is based on the same enthesitis assessment we performed within the FUTURE 2 PsA trial (CAIN457F2312) in the form of the LEI which is composed of three different enthesial sites (Lateral epicondyle, left and right; medial femoral condyle, left and right; Achilles tendon insertion, left and right). Within this trial, the resolution of enthesitis amongst those patients with these symptoms at Baseline has been assessed for Week 24:

Week 24, the end of the placebo-controlled phase:

- Secukinumab (300 mg): 48.2% of patients.
- Secukinumab (150 mg): 42.2% of patients.
- Placebo: 21.5% of patients.

In addition to these clinical data we can make the following assumptions:

- There is no difference in response to secukinumab between the different enthesis sites assessed as part of the LEI in the FUTURE 2 trial. Therefore we do not expect a different response when we only assess the Achilles tendon insertion.
- There is no difference in secukinumab response rates regarding resolution of enthesitis between PsA and axPsA patients. Therefore we pool the analysis for both diseases.

A total of 89 patients per arm are required to achieve 90% power to detect a difference on a two-sided, 2.5% significance level, if the true response rates are 45% under secukinumab and 21% under placebo. To account for some drop-outs and other protocol violations, 100 patients per arm = 200 patients total should be randomized into this trial.

For the comparison within the 2 subgroups of PsA and axPsA patients, which will consist of 50% of the total study population each, the trial will have about 46% power with regard to the primary endpoint.

No sample size justification is provided for secondary analyses, hence results from secondary analyses should be interpreted carefully.

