## 5.4 Statistical models

### 5.4.1 Primary analysis

The primary analysis will be performed comparing treatments with respect to the primary efficacy variable in a logistic regression model with the factors treatment, country and stratification factor diagnosis (PsA or axSpA).

```
Proc logistic data=aaa;  
Class TRT COUNTRY STRATA / param=glm;  
Model AVAL = TRT COUNTRY STRATA;  
Lsmeans TRT / diff cl exp;  
Ods output diffs=lsm_diff;  
Run;
```

In cases where separation is a concern for the primary endpoint at Week 24, e.g. 0% or 100% response in one treatment (sub)group, an exact logistic regression model will be applied to all visits. To ensure convergence, this model will not include any continuous covariates.

SAS Code for Logistic model:

```
Proc logistic data=aaa exactonly;  
Class TRT STRATA / param=glm;  
Model AVAL = TRT STRATA;  
Exact TRT / estimate=both;  
Ods output exactoddsratio=exactoddsratio;  
Run;
```

For subgroup analysis, the above code will be used for each stratification factor.

The primary model will also be recalculated with the above factors included as well as with respective terms for a subgroup\*treatment interaction.

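### The primary logistic model, overall and in both confirmatory subgroups, uses no baseline severity covariate; prespecifying baseline heel pain would cost almost nothing and could recover some power (an efficiency gain, not a validity error)

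*SAP*

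**What the plan says.** SAP 2.5.2 and 5.4.1 fit the Week 24 response "in a logistic regression model with the factors treatment, country and stratification factor diagnosis (PsA or axSpA". Protocol 9.4.2 also puts the "primary efficacy variable in a logistic regression model with the factors treatment", but its other two factors are TNFα inhibitor status and diagnosis. SAP section 4 records no change from the protocol. Both documents reuse the model for the separate PsA and axSpA tests, and the SAP drops the diagnosis factor there. Those two tests belong to the confirmatory strategy (protocol 9.5.1.7, SAP 2.5.2).

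The continuous endpoints are treated differently. Heel pain is analysed by ANCOVA "with covariate baseline measurement of heel pain", and the four global assessments and SF-36 likewise carry their own baseline value. The logistic models for LEI resolution and bone marrow oedema in SAP 2.7.2 contain factors only.

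Baseline severity enters the primary endpoint only as a subgroup factor (protocol 9.4.4, SAP 2.2.1) and through an optional refit: the protocol says the primary model "may also be recalculated with these factors included". Protocol Table 6-1 schedules heel pain, LEI and both heel-enthesiopathy scales at Baseline.

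**The concern.** Including a prognostic baseline covariate in a logistic model generally raises the power of the treatment test and adjusts for chance imbalance in that covariate. Randomization is stratified by diagnosis only, so balance in severity is left to chance. Entry criteria are broad: heel pain of at least one month with no upper limit on duration and, in PsA, one tender and one swollen joint suffice.

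The overall test has power to spare. The two subgroup tests do not. Protocol 9.8 gives them about 58% power and SAP section 3 about 46%. Precision is scarcest there, and a variable that might add some is already being collected. The optional refit in protocol 9.4.4 does not change the confirmatory p-value.

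**Working it through.** **Inputs.** Protocol 9.8 gives its power "if the true response rates are 45% under secukinumab and 21% under placebo". On that basis it sets the trial size: "A total of 89 patients per arm are required to achieve 90% power to detect a difference on a two-sided, 5% significance level". Protocol 3.1 gives 1:1 allocation. SAP section 3 keeps 89 per arm but at a "two-sided, 2.5% significance level", a separate discrepancy. The prognostic strength of baseline heel pain is not in the documents and is **assumed**.

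**Step 1: reproduce the plan's figures (two-sided 5%).** With p1 = 0.45, p0 = 0.21, difference d = 0.24 and mean rate 0.33:

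- n = [1.960·√(2·0.33·0.67) + 1.282·√(0.45·0.55 + 0.21·0.79)]² / 0.24² = 78.6, so 79 per arm.
- With continuity correction, n' = (n/4)·[1 + √(1 + 4/(n·d))]² = (78.6/4)·[1 + √(1 + 4/(78.6·0.24))]² = 86.7, so 87 per arm, close to the stated 89. Corrected power at 89 per arm is 90.8%.
- Subgroup at 44 per arm, corrected: z = (0.24 − 1/44 − 1.960·√(0.4422/44)) / √(0.4134/44) = 0.214, so 58.5%. At 45 per arm it is 59.7%. The stated figure is 58%.
- Without the correction, 45 per arm gives 68.3%. This is why the simulated starting values below lie about ten points above the stated 58%: a Wald test carries no continuity correction.

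**Step 2: simulate with and without a covariate.** One standard normal baseline covariate; intercepts solved so that the marginal rates stay at 45% and 21%; Wald test at two-sided 5%; 6,000 trials per cell. Country and TNFα status are left out of both models. Power in %, without → with the covariate:

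| Assumed OR per SD | Overall, 89/arm | Overall, 100/arm | Subgroup, 45/arm | Subgroup, 50/arm |
|---|---|---|---|---|
| 1.00 | 93.7 → 93.5 | 95.3 → 95.1 | 68.8 → 68.7 | 73.1 → 73.4 |
| 1.28 | 92.7 → 93.1 | 95.3 → 95.3 | 69.5 → 69.7 | 72.6 → 73.6 |
| 1.65 | 93.4 → 94.3 | 95.6 → 96.3 | 68.4 → 70.3 | 71.7 → 74.8 |
| 2.12 | 93.5 → 95.3 | 95.3 → 97.0 | 68.5 → 72.0 | 72.2 → 77.3 |
| 2.72 | 93.5 → 96.6 | 95.5 → 97.8 | 68.9 → 75.1 | 72.2 → 79.7 |
| 4.48 (extreme) | 92.8 → 98.1 | 95.3 → 99.0 | 68.4 → 80.5 | 71.4 → 84.5 |

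The Monte Carlo standard error of a single power is about √(0.7·0.3/6000) = 0.6 points in a subgroup and √(0.935·0.065/6000) = 0.3 points overall. The changes at OR 1.00 are therefore noise. The 100 and 50 per arm columns correspond to the full planned enrolment, which the FAS largely keeps because drop-outs are classified rather than removed.

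**Step 3: carry the gain to the stated 58%.** Let r = (z_adj + 1.960)/(z_unadj + 1.960), with z the normal quantile of each power at 45 per arm. New power = Φ[r·(z(0.58) + 1.960) − 1.960], with z(0.58) = 0.202.

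- OR 1.65: r = (0.533 + 1.960)/(0.479 + 1.960) = 1.022, giving Φ(0.250) = 60%.
- OR 2.72: r = (0.678 + 1.960)/(0.493 + 1.960) = 1.075, giving Φ(0.365) = 64%.

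**The case against.** The case for leaving the model alone has real content.

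- **The contrast with the ANCOVA endpoints is not like for like.** Those adjust for the endpoint's own baseline. The Achilles item is scored present or absent, and tenderness there is an entry criterion, so its own baseline barely varies (one or two tender sides at most). A reader might infer that the plan breaks its own rule; it does not, since all three binary models consistently use factors only. This stands. It does not argue against a different covariate that does vary, such as the heel pain NRS.
- **No document shows that heel pain predicts resolution on palpation.** This stands: the gain is conditional. At OR 1.28 or below it is essentially nil, and overall it is under 1 point up to OR 1.65.
- **The subgroups stay underpowered.** True: 60% to 64% is still low.
- **Severity is partly handled** by the subgroup analyses and the optional refit, and a redacted SAP heading after 2.5.3 may hide further supportive work. None of this would alter the primary model.
- **The change has side effects.** A subgroup has only about 33 expected responders (50 × 0.45 + 50 × 0.21), already shared with country terms. The odds ratio that defines success becomes conditional on the new covariate. The SAP's exact-logistic fallback excludes continuous covariates, and a missing baseline would drop a patient from the fit. Each is a fair point, and each of the last three can be met with a sentence. The odds ratio is already conditional on the factors in the model, and the null of no effect is unchanged.

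**Conclusion.** The omission is a fact; its cost is conditional. Over an assumed odds ratio per SD of 1.0 to 2.7, the power forgone is about 0 to 3 points overall at 89 per arm and about 0 to 6 points per subgroup at 45 per arm (up to about 7.5 at 50 per arm). Only the extreme value of 4.48 yields more, about 5 overall and 12 to 13 per subgroup. The figures assume a normally distributed covariate and no other factors in the model.

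Two stronger readings are tempting and not supported. One is that the primary test is wrong or biased: it is valid as planned. The other is that power is certainly being lost: that needs a prognostic strength which neither document gives.

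The case rests on asymmetry: a negligible loss if the covariate is useless, against a few points in the two weakest confirmatory tests if it is not. LEI resolution is exploratory (SAP 2.7.2), so the same omission there affects no confirmatory conclusion.

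**What to change.** Protocol 9.4.2 (TNFα inhibitor status) and SAP 2.5.2/5.4.1 (country) must be reconciled in any case. In the same edit, and before the Week 24 lock unblinds the sponsor:

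- Add baseline heel pain NRS as one prespecified continuous covariate to the overall model and both subgroup models.
- State a simple rule for a missing baseline that keeps every FAS patient in the fit, for example substituting the mean baseline over all patients regardless of arm.
- Note that the reported odds ratio is conditional on the covariate.
- Leave the exact-logistic fallback without it.
- Keep the model without the covariate as a sensitivity analysis.

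Optional and minor: add the baseline number of tender sites to the exploratory LEI-resolution model, counted over the same sites as the analysed LEI. The SAP uses four sites and protocol 6.4.1.1 six, so that must be settled first.

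The cost is a few sentences in each document and one model term. No new data are needed.

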#### **5.4.2 Key secondary analysis**

Not applicable

#### **5.4.3 Secondary analysis**

Categorical variables will be analyses using the logistic model, code is described above.

Endpoints with continuous data type expected to be normally distributed will be analyzed using an analysis of covariance (ANCOVA) model with treatment and baseline stratification factor, country and baseline value as covariate. Confidence intervals for the difference between each dose of secukinumab and placebo will be calculated.

SAS code for ANCOVA:

```
proc mixed data=aaa;  
class TRT COUNTRY STRATA;  
model response = TRT STRATA COUNTRY BASE / s;  
lsmeans TRT / diff;  
run;
```

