5.2 Treatment arms

Patients will be randomized to one of the following 2 treatment groups in a 1:1 ratio as depicted below:

- Group 1: secukinumab 150 mg/300 mg s.c.: secukinumab as 1 (1.0 mL PFS of 150 mg dose) s.c. or 2 (2 × 1.0 mL PFS of 150 mg dose, 300 mg) s.c. injections at Baseline, Weeks 1, 2, and 3, followed by administration every 4 weeks starting at Week 4.
 - PsA patients, who have been previously exposed to TNF blockers, and/or with concomitant moderate to severe plaque psoriasis receive 2 (two) 1.0 mL PFS of 150 mg dose (i.e. 300 mg) s.c..
 - Other PsA patients and axSpA patients receive 1 (one) 1.0 mL PFS of 150 mg dose s.c..
- Group 2: placebo s.c. followed by secukinumab 150 mg/300 mg s.c. at Baseline, Weeks 1, 2, and 3, followed by administration every 4 weeks starting at Week 4.2
 - PsA patients, who have been previously exposed to TNF blockers, and/or with concomitant moderate to severe plaque psoriasis receive placebo as 2 (two) 1.0 mL PFS s.c..
 - Other PsA patients and axSpA patients receive placebo as 1 (one) 1.0 mL PFS s.c..
 - At Week 24, all patients in Group 2 will switch to their pre-assigned secukinumab treatment

Patients will receive study treatment at Baseline, Weeks 1, 2, and 3, followed by treatment every 4 weeks through Week 52 (last dose given at Week 48). At Week 24, patients originally randomized to placebo will switch to receive secukinumab 150 mg (1 injection of secukinumab 1 mL/150 mg) or secukinumab 300 mg (2 injections of secukinumab 1 mL/150 mg) in open-label fashion without a loading regimen. Blinding to the original treatment assignment will be maintained until after the Week 52 database lock and analyses are completed (see Section 5.4). Patients will self-administer all secukinumab and placebo doses as described in Section 3.1 at the study site or at home at indicated study visits (see Table 6-1) through Week 52.

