### 1.1 Study design

This is a 52-week, randomized, parallel-group, double-blind, multicenter, international study consisting of an 8-week screening period, a 24-week, placebo-controlled, double-blind treatment period and a 28-week open-label treatment period in patients with PsA and axSpA.

The dosing of secukinumab will be applied according to the approved European Summary of Product Characteristics (SmPC) in PsA and AS disease. According to SmPC, patients with AS and PsA (with concomitant none-to-mild psoriasis) will receive 150 mg secukinumab or placebo (1 PFS) where as only PsA patients with concomitant moderate-to-severe-psoriasis will receive 300 mg of secukinumab or placebo (2 PFS). In case of axSpA patients with objective signs of inflammation at screening, evident by either MRI with Sacroiliac joint inflammation (according to source documentation) and/or hsCRP > upper limit of normal (ULN, as defined by central lab) , secukinumab/placebo will be applied as 1 (1.0 mL pre-filled syringe (PFS) of 150 mg dose) s.c. injection.

The study design is given in Figure 1.

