### **2.8.1 Adverse events (AEs)**

The crude incidence of treatment emergent adverse events (i.e. events started after the first dose of study treatment or events present prior to the first dose of study treatment but increased in severity based on preferred term) will be summarized by primary system organ class and preferred term. Confidence intervals for the crude rate will be derived as described in Section

In addition, exposure time-adjusted rates (incidence rate) including 95% confidence intervals will be provided for the entire treatment period to adjust for differences in exposure between treatment groups. Graphical displays of the crude incidence and exposure-adjusted rates will be presented for all AEs and serious AEs by system organ class.

Treatment emergent adverse events reported will be presented by preferred term in descending frequency according to its incidence in total secukinumab group (combining all secukinumab treatment groups) starting from the most common event. Summaries (crude incidences only) will also be presented for AEs by severity and for study treatment related AEs. If a particular AE 'severity' is missing, this variable will be listed as missing and treated as missing in summaries. If a subject reported more than one adverse event with the same preferred term, the adverse event with the greatest severity will be presented. If a subject reported more than one adverse event within the same primary system organ class, the subject will be counted only once with the worst severity at the system organ class level, where applicable.

Separate summaries will be provided for

- adverse events suspected to be related to study drug by the investigator
- deaths
- serious adverse events
- adverse events leading to discontinuation
- adverse events leading to temporary dose interruption

Adverse events will also be reported separately by MedDRA SMQ.

For all adverse event summaries, the MedDRA version used for reporting the study will be described in a footnote.

Adverse event summaries will also be provided for the follow-up period for all patients (completers and early discontinuations).

A listing of non-treatment emergent adverse events will be provided. These cover adverse events that occurred before the first dose of the study treatment. The crude incidence will be provided without treatment information.

Algorithms for date imputations will be provided in Programming Specifications.

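### SAP 5.4.3 promises an interval for each secukinumab dose against placebo, although dose is not randomised and no dose-matched placebo comparator is defined

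*SAP*

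**What the plan says.** **The commitment.** SAP 5.4.3 describes the ANCOVA for continuous secondary endpoints and then says: "Confidence intervals for the difference between each dose of secukinumab and placebo will be calculated".

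**What is randomised.** Protocol 3.1: "Randomization will occur to 1 of the following 2 treatment groups in a ratio of 1:1". Protocol 5.3 stratifies by diagnosis alone.

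**How dose is set.** Protocol 5.2, secukinumab arm: "PsA patients, who have been previously exposed to TNF blockers, and/or with concomitant moderate to severe plaque psoriasis receive 2 (two) 1.0 mL PFS", and "Other PsA patients and axSpA patients receive 1 (one) 1.0 mL PFS of 150 mg dose s.c". The placebo arm follows the same rule, so patients there "with concomitant moderate to severe plaque psoriasis receive placebo as 2 (two) 1.0 mL PFS s.c" (as do PsA patients with TNF-blocker exposure), and the others receive one syringe. SAP 1.1 states the rule differently: "only PsA patients with concomitant moderate-to-severe-psoriasis will receive 300 mg of secukinumab or placebo (2 PFS". It does not mention TNF history.

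**What the endpoint paragraphs specify.** SAP 2.7.2 (heel pain and both physician VAS scores) and SAP 2.11 (both patient VAS scores and SF-36) each name one treatment factor and one adjusted mean difference, as do protocol 9.5.1.1, 9.5.1.3 and 9.5.1.4. The code in SAP 5.4.3 has one TRT factor plus diagnosis stratum, country and baseline value. SAP section 4 reports no change from the protocol's analyses.

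**The concern.** Dose is a consequence of who the patient is. The 300 mg group consists only of PsA patients with a particular skin or treatment history. The 150 mg group is everyone else, including all axSpA patients. The placebo arm contains both kinds. Setting each dose against that whole arm compares a selected group with an unselected one. The diagnosis term removes the PsA–axSpA part of the imbalance but leaves psoriasis extent and TNF history within PsA untouched. The protocol itself treats TNF-inhibitor status as relevant to outcome: it is a factor in the primary model (9.4.2) and a planned subgroup (9.4.4, 9.5.1.6).

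A programmer who meets the sentence must either ignore it or recode TRT as placebo, 150 mg and 300 mg. With that recoding, the difference option already in the code would also print a 300 mg versus 150 mg contrast. Readers could take such output as dose-response evidence, which this design cannot supply.

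**Working it through.** No figure in either document bears on these contrasts, so there is nothing of the plan's own to reproduce. The check asks what the 5.4.3 model returns when TRT has three levels and the true effect is the same at both doses.

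**Inputs from the documents.** Allocation 1:1 (protocol 3.1); about half PsA and half axSpA (protocol 5.3); all axSpA patients in the one-syringe class (protocol 5.2); adjustment for diagnosis (SAP 5.4.3).

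**Assumptions, not in the documents.**
- A share q of PsA patients is in the two-syringe class: 30%, 50% or 70%.
- That class has an outcome shift g, the same in both arms: 0.2 or 0.5 residual SD.
- Baseline value and country are unrelated to dose class.

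**Step 1: the five cells** (relative size; share of the cell in the two-syringe class)
- axSpA placebo: 1; 0
- axSpA 150 mg: 1; 0
- PsA placebo: 1; q
- PsA 150 mg: 1 − q; 0
- PsA 300 mg: q; 1

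**Step 2: what the diagnosis term absorbs.** The 300 mg cell is fitted exactly by its own coefficient. The diagnosis coefficient is therefore the weighted PsA–axSpA difference within placebo (difference q, weight 1/2) and within 150 mg (difference 0, weight (1 − q)/(2 − q)):

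c = 0.5q / [0.5 + (1 − q)/(2 − q)]

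**Step 3: bias left in each contrast.**
- 300 mg minus placebo: g × [1 − (q + c)/2]
- 150 mg minus placebo: −g × (q − c)

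Worked case, q = 0.5:
- c = 0.25 / (0.5 + 0.3333) = 0.30
- 300 mg multiplier: 1 − 0.80/2 = 0.60
- 150 mg multiplier: −(0.50 − 0.30) = −0.20

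**Step 4: results (residual SD).** The last column is the 300 mg bias minus the 150 mg bias.

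| q | c | g | 300 mg bias | 150 mg bias | Spurious dose gap |
|---|---|---|---|---|---|
| 0.3 | 0.165 | 0.2 | +0.154 | −0.027 | 0.181 |
| 0.3 | 0.165 | 0.5 | +0.384 | −0.068 | 0.452 |
| 0.5 | 0.300 | 0.2 | +0.120 | −0.040 | 0.160 |
| 0.5 | 0.300 | 0.5 | +0.300 | −0.100 | 0.400 |
| 0.7 | 0.479 | 0.2 | +0.082 | −0.044 | 0.126 |
| 0.7 | 0.479 | 0.5 | +0.205 | −0.111 | 0.316 |

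A large-sample simulation of the same model, with baseline included and country omitted, gave 0.08 to 0.39 for 300 mg and −0.02 to −0.12 for 150 mg, which agrees within simulation error.

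**Step 5: the matched comparison.** Adding a baseline syringe-class term, so that each dose is judged against placebo patients of the same class, brought both biases to within 0.01 SD of zero in the simulation. That is expected, because within a class allocation to secukinumab or placebo is random.

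**Step 6: size of the matched groups.** With 200 patients, about 100 have PsA. The two-syringe class would then hold about 30 to 70 patients, or 15 to 35 per arm.

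**The case against.** The strongest reply is that this is a stray sentence and not a planned analysis. Each continuous endpoint has its own paragraph with one pooled difference, the code has one treatment factor, and the SAP defines two treatment groups. It contains other generic text, such as a reference to pooled DMC analyses in 2.8.4.1 although protocol 8.4 requires no DMC. This stands: most of the plan yields a single contrast, and it would be too strong to say that the report will show dose-specific effects.

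A reader might find proof of intent in SAP 2.8.1, where adverse events are ordered by incidence "in total secukinumab group (combining all secukinumab treatment groups"). The documents do not support that. It is a sorting rule for safety tables, and the phrase may equally mean patients on secukinumab from baseline together with those switched at Week 24. Protocol 3.3 does list 150 mg and 300 mg regimens as treatment groups, but it defines no dose comparison.

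A reader might also infer that the intervals are confounded on any reading. They are not. The sentence does not say which placebo patients serve as comparator, and each dose against placebo of the same syringe class would be a randomised comparison. What the text shows is an undefined comparator; the bias belongs to the whole-arm reading.

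Nor can TNF history be taken as a settled source of confounding under the SAP. The SAP sets dose by psoriasis only, and its deviation table treats prior TNF-inhibitor use as a deviation (INCL16, EXCL09). The TNF component comes from the protocol.

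Finally, the secondary endpoints are exploratory (SAP 2.7.2), and SAP section 3 advises caution in interpreting them. That limits the impact, but exploratory status concerns error control and does not remove confounding from a reported interval.

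**Conclusion.** The sentence is wrong for this design as written, with limited impact. It promises by-dose intervals without defining a dose factor or comparator, and it contradicts the pooled analysis specified elsewhere in both documents.

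On the whole-arm reading, and under the assumed ranges for q and g, the bias is roughly 0.1 to 0.4 SD for 300 mg and up to about 0.1 SD the other way for 150 mg. Because the two move apart, a dose difference would appear where none exists. These sizes rest wholly on the assumptions; the documents supply neither the share of PsA patients in the two-syringe class nor its prognosis. The direction is also assumed: if that class improves less in both arms, 300 mg looks worse and 150 mg better, and the reverse if it improves more. No bias in millimetres or score points can be derived from the documents.

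Six exploratory endpoints are concerned: heel pain, four global assessments and SF-36. The primary endpoint, the logistic models and the confirmatory testing strategy are untouched.

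**What to change.** Replace the sentence in SAP 5.4.3 with one that names a single contrast, for example: *For each continuous endpoint, report the 95% confidence interval for the adjusted mean difference between all patients randomised to secukinumab and all randomised to placebo.* State that TRT has two levels.

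If by-dose results are wanted, compare one-syringe secukinumab with one-syringe placebo, and two-syringe with two-syringe, using the class assigned at baseline. Label them descriptive subgroups and draw no inference between 150 mg and 300 mg, because that comparison is not randomised even after matching.

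Before any by-dose output is programmed, the passages that define the dose classes must be reconciled. SAP 1.1 uses psoriasis alone; protocol 5.2 adds prior exposure to TNF blockers; protocol 3.3 refers to inadequate response to them.

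The cost is one SAP sentence, plus the reconciliation if by-dose summaries are kept. No extra data are needed, since placebo patients already have a pre-assigned dose class (protocol 5.2).
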